4. PROPOSED RESEARCH SCHEDULE

Research Activities

[figure not shown]
Activities	Start Date	End Date
Systematic review. Research and methodology classes	07/09/2021	06/03/2022
Baseline recruitment, collection of FBS, anthropometric measurements and lifestyle habits; distribute 24- hour CGMS	07/03/2022	06/11/2022
Second visit, collection of FBS, anthropometric measurements and lifestyle habits; distribute 24-hour CGMS	07/11/2022	06/07/2023
Third visit, collection of FBS, anthropometric measurements, lifestyle habits and collect the 24-hour CGMS	07/07/2023	06/03/2024
data key in, data analyses to investigate the optimal-meal-timing, anthropometric measurements, lifestyle habits and the associations between these variables; publication	07/03/2024	06/09/2024

Milestones

Activities	Date	Cumulative Project Completion Percentage (%)
Completion of systematic review to study optimal-meal-timing, chrononutrition, lifestyle factors and	31/03/2022	10

anthropometric measurements in prediabetes individuals		
Baseline recruitment completed, by using convenient sampling method. OGTT, FBS and HbA1c traced from medical record. Anthropometric measurements and lifestyle habit information collected. 3- day food diary and CGMS distributed.	30/11/2022	35
Second visit completed. Anthropometric measurements and lifestyle habit information collected. 3-day food diary and CGMS distributed.	31/07/2023	60
Third visit completed. OGTT, FBS and HbA1c traced from medical record. Anthropometric measurements and lifestyle habit information collected. 3-day food diary and CGMS collected	31/03/2024	85
Data key in, data analyses and publication	31/08/2024	100

Gantt Chart of Research Activities with Milestones

5. References

hemoglobin A1c in prediabetes individuals. *The Journal of Biological and Medical Rhythm Research* 34(3): 393-402.

APPENDIX B: SOCIO-DEMOGRAPHY

Date of interview: / / / / / / /

d d / m m m / y y y y

Section 1.0 Socio-demography

1.1 What is the **highest level of education** that you have completed?

0: None (*skip to Q1.3*)

1: Primary (eg. PSLE)

2: Secondary (eg. GCE 'O' / 'N' level)

3: Junior College / Centralised Institute (GCE 'A' Level / International Baccalaureate)

4: Institute of Technical Education [ITE/NTC (NITEC, higher NITEC or equivalent)]

5: Diploma/ Advanced diploma / Polytechnic

6: Trade or work qualification not from university

7: University Bachelor's Degree / Postgrad Diploma / Professional Degree

8: Postgraduate (Master Degree / Doctorate)

1.2 How many **years of education** have you received? (*Including home schooling but excluding pre-school, kindergarten or years spent repeating individual grades*)

years

months

1.3 What is your current job status?

0: Not employed (*skip to Q1.5*)

1: Self-employed

2: Part-time employed

3: Full-time employed

1.4 During the past 1 month, did you require to work **overtime** (until after 7pm)?

0: No

1: Less than once a week

2: Once or twice a week

3: Three or more times a week

1.5 What was your weight before prediabetes diagnosis ?

 .

1.6 What is your ethnic group?

0: Chinese

1: Malay

2: Indian

3: Other, please specify: _____

Section 2.0 Lifestyle

2.1 Have you smoked in the past?

0: Not at all for entire life

1: Yes, but stopped smoking before conceiving for this pregnancy

2: Yes, but stopped smoking since conceived for this pregnancy

3: Yes, but stopped smoking 1 month ago

4: Yes, during the past 1 month and/ or currently smoking

2.2 During the **past 1 month**, did anyone **smoke in indoor areas** where you work and/ or stay? (Excluding area which are not fully enclosed. Should answer 'yes' if smelling the smoke).

0: No

1: Yes

2.3 How often did you have a drink containing **alcohol** during the **past 3 months before conceiving** for this pregnancy? (Including traditional wine, e.g. Youmeishu, DOM Benedictine)

0: never or less than once per month

1: 1-3 times per month

2: 1-2 times per week

3: 3-4 times per week

4: 5-6 times per week

5: 1 time or more per day

2.4 Have you consumed any drink containing **alcohol since your current pregnancy**? (Including traditional wine, e.g. Youmeishu, DOM Benedictine)

0: No

1: Yes, but stopped drinking 1 month ago

2: Yes, current and during the past 1 month

2.5 Did you take any pills, tonics or tablets to **supplement** your diet (e.g. vitamin, minerals, iron tablets, folic acid, fish oils etc.)? (can be more than 1 options, except if selecting 'Never')

0: Never or without supplement for at least 3 months ago before conceiving for this pregnancy

1: Yes, since 3 months before conceiving for this pregnancy
 2: Yes, since conceived for this pregnancy
 3: Yes, current and during the past 1 month

2.6 **During the past 1 month**, how often did you **skip** your breakfast, lunch and dinner?

	Breakfast	Lunch	Dinner
--	-----------	-------	--------

0: never
 1: 1-3 times per month
 2: 1-2 times per week
 3: 3-4 times per week
 4: 5-6 times per week
 5: Every day

2.7 **During the past 1 month**, how often did you **delay** your breakfast, lunch and dinner for more than 2 hours from your regular meal timings?

	Breakfast	Lunch	Dinner
--	-----------	-------	--------

0: never
 1: 1-3 times per month
 2: 1-2 times per week
 3: 3-4 times per week
 4: 5-6 times per week
 5: Every day

2.8 **During the past 1 month**, how often did you have **snack(s) taken after 7pm**? (Snack is defined as a portion of food often smaller than a regular meal, including beverage such as milk. Snacking frequency is defined with a time interval between episodes of at least 15 min)

0: never

1: 1-3 times per month
 2: 1-2 times per week
 3: 3-4 times per week
 4: 5-6 times per week
 5: 1 time per night
 6: 2 or more times per night

APPENDIX C
International Physical Activity Questionnaire

Project Name:

Meal Timing and Glucose Tolerance

Date of interview:

		/				/			
d	d		m	m	m		y	y	y

3.0 Physical activity

I am going to ask you about the time you spent being physically active. Think about only those physical activities that you did for at least 10 minutes at a time over the past week.

During the last 7 days, how many days have you done the following kind of physical activities?

3.1 Vigorous physical activities which take hard physical effort and make you breathe much harder than normal. (E.g. heavy lifting, aerobics, fast swimming or fast bicycling)

days in last 7 days

(If answers '0', skip to Q 3.2)

3.1.1 On average about how much time did you usually spend on those activities?

hrs

mins per day

(or)

hrs

mins per week

3.1.2 During which period(s) of the day did you usually perform those activities? (Can be more than 1 options)

- 1: Early morning (5am – 6:59am)
- 2: Morning (7am – 11:59am)
- 3: Afternoon (12pm – 4:59pm)
- 4: Evening (5pm – 6:59pm)
- 5: Night (7pm – 11:59pm)
- 6: Late-night (12am – 4:59am)

3.2 Moderate physical activities which take moderate physical effort and make you breathe somewhat harder than normal. (E.g. carrying light loads, sweeping, scrubbing floors, washing windows, dancing, or bicycling/swimming at a regular pace. Do not include walking)

days in last 7 days

(If answers '0', skip to Q 3.3)

3.2.1 On average about how much time did you usually spend on those activities?

hrs

mins per day

(or)

hrs

mins per week

3.2.2 During which period(s) of the day did you usually perform those activities? (Can be more than 1 options)

- 1: Early morning (5am – 6:59am)
- 2: Morning (7am – 11:59am)
- 3: Afternoon (12pm – 4:59pm)
- 4: Evening (5pm – 6:59pm)
- 5: Night (7pm – 11:59pm)
- 6: Late-night (12am – 4:59am)

3.3 How many days did you walk for at least 10 minutes at a time? (Includes at work and at home, walking from place to place, and any other walking that you have done solely for recreation, sport, exercise, or leisure)

days in last 7 days
 (If answers '0', skip to Q 4.1)

3.3.1 On average about how much time did you usually spend on walking?

hrs mins per day (or) hrs mins per week

3.3.2 During which period(s) of the day did you usually spend on walking? (Can be more than 1 options, select as appropriate)

- 1: Early morning (5am – 6:59am)
- 2: Morning (7am – 11:59am)
- 3: Afternoon (12pm – 4:59pm)
- 4: Evening (5pm – 6:59pm)
- 5: Night (7pm – 11:59pm)
- 6: Late-night (12am – 4:59am)

Section 4.0 Sedentary behaviour

The following questions are about time spent **sitting or lying down while being awake, at least 10 minutes** at a time over the past week. This may include time spent sitting at a desk, visiting friends, reading or sitting or lying down to watch television.

4.1 [For those who previously answered Yes to work]

During the last week, on an average **working day**, how much time did you spend **sitting at work**?

hrs mins per day

4.1.1 During the last week, on an average **working day**, how much time did you spend on **electronic devices such as social media, computer, tablet, mobile phone at work?**

hrs mins per day

4.2 [For those who previously answered Yes to work]

Excluding any time at work, during the last week, on average how much time did you spend.....

[For those who previously answered No to work]

During the last week, on average how much time did you spend.....

4.2.1 sitting or lying down and **watching television?**

hrs mins per day
 (or)
 hrs mins per week

4.2.2 sitting or lying down and viewing **electronic devices** other than television in your leisure time (e.g watching online video, internet surfing, social media, electronic games on computer, tablet or mobile phone etc.)? Do not include time spent on computer at work.

hrs mins per day
 (or)
 hrs mins per week

4.2.3 sitting or lying down at **mealtimes, driving or reading** or other time sitting [excluding TV /electronic device time]

hrs mins per day
 (or)
 hrs mins per week

1 **Section 5.0 Electronic media use before bedtime**

 2 During the last 7 days, on average how much time did you spend on the below electronic devices **before going to sleep in bed at night** (after 3 7pm)?

Electronic devices	How many days in past week (0-7)	Duration per day or per week (If the durations of using the device are inconsistent every night, sum up the duration spent for each night to obtain total time spent per week)	Used in bedroom 0: No ; 1: Yes
5.1 Television		 hrs  mins per day	
5.2 Computer: surfing, online video, playing, reading		 hrs  mins per day	
5.3 Computer: movie, TV series		 hrs  mins per day	
5.4 Tablet/ mobile phone: surfing, online video, playing, reading, texting		 hrs  mins per day	
5.5 Tablet/ mobile phone: movie, TV series		 hrs  mins per day	
5.6 Tablet/ mobile phone: talking only		 hrs  mins per day	
5.7 Audio player (music, radio)		 hrs  mins per day	
5.8 Gaming console		 hrs  mins per day	
5.9 Partner's media use		 hrs  mins per day	

 4 **Reference:** See [name] Loy, [name] Bun Cheung, Mary Chong, Falk Müller-Riemenschneider, Ngee Lek, YS Lee, Kok Hian Tan, Bernard Chern, Fabian Yap, Jerry

 5 Chan. 2019. Maternal night-eating pattern and glucose tolerance during pregnancy: study protocol for a longitudinal study. *BMJ Open*. 9:e030036.

6 doi:10.1136/bmjopen-2019-030036.

APPENDIX D
Munich Chronotype Questionnaire

8

9

Meal Timing and Glucose Tolerance

10

Project Name:

		/				/					11
d	d		m	m	m		y	y	y	13	12

13

14

15

16

Munich Chronotype Questionnaire (MCTQ)

17

18

This questionnaire requires you to report your sleep patterns over the past 4 weeks. Working day and non -working day sleep patterns were asked separately. Please answer this question according to your perceptions of your weekly habits, workday sleep patterns and non -working days.

[figure not shown]
23

I have regular working hours (this includes housewives):

24

 Yes, I work	 1	 2	 3	 4	 5	 6	 7		Day/week
 No									

If your answer is 'Yes, 7 days' or 'No', please consider whether your bedtime may differ between normal weekdays and weekends and fill out the MCTQ accordingly.

26

27

Based on the following picture, answer the question below (Please answer on a 24 -hour scale, for example; 23:00):

30

Working Days		
Picture 1	I entered the bedroom at: _____	
Picture 2	Some people stay awake even after lying in bed.	
Picture 3	I'm ready to go to bed at (turn off the lights and go to sleep): _____	
Picture 4	How many minutes do I need to sleep: _____	
Picture 5	I woke up in the morning at: _____	
Picture 6	I got out of bed after a few minutes: _____	
I use an alarm clock on weekdays		Yes  No
If YES, I usually wake up BEFORE the alarm clock rings:		Yes  No
Weekend		
Picture 1	I entered the bedroom at: _____	
Picture 2	Some people stay awake even after lying in bed.	

Picture 3	I'm ready to go to bed at (turn off the lights and go to sleep): _____			
Picture 4	How many minutes do I need to sleep: _____			
Picture 5	I woke up in the morning at: _____			
Picture 6	I got out of bed after a few minutes: _____			
My waking hours were due to the use of an alarm clock (Figure 5):		Yes		No
There are certain reasons I can't determine my bedtime independently on holidays:		Yes		No
If 'Yes', among the factors are				
Child/husband/pet				
Hobby				
Solat/morning prayer/meditation				
Others (please state): _____				
Will I go back to sleep after doing the activity, on holidays?				
Yes		No		
If 'Yes' to the previous question, what time do you go to bed and wake up?				
Time to sleep again: _____				
Time to wake up again: _____				

31

32

33

34

35

36

37

38

39

40

41

42

43

44

45

46

47

48

49 Reference:

50

51 [name] Mazri, Zahara Abdul Manaf, Suzana Shahar, Arimi Fitri Mat Ludin, Norwahidah Abdul Karim,
 52 Andrea Yu-Lin Ban & Rose Azzlinda Osman (2021): Modified Munich chronotype questionnaire for application to
 53 short-interval split sleep of non-shift workers, Chronobiology International, DOI:
 54 10.1080/07420528.2021.1887209

APPENDIX E

Project Name:

Date of interview:

[figure not shown]
Three Days Dietary Record

Meal Timing and Glucose Tolerance

		/				/					60
d	d		m	m	m		y	y	y	y	

61 3 days dietary record guidelines:

[figure not shown]
1. Please fill in this food intake log book as completely as possible for 2 weekdays and 1 weekend.
2. Subjects were not allowed to change food habits while food intake records were being conducted.
3. For food records, please indicate the time, type and quantity/ size of all food and beverages taken immediately after meal time.
4. If you have any further enquiry, please contact:
 [name] [name] [contact]

71 Household Measurements
A) Spoons

84 Teaspoon Table Spoon Table Spoon
 10ml 10ml 10ml
 85 Scoop 30ml Scoop 15ml Scoop 80ml Table Spoon
 86 20ml

B) Plate and Bowls

97
 98
 99
 100
 101
 102
 103
 104
 105
 106
 107
 108
 109
 110
 111
 112
 113
 114
 115
 116
 117
 118
 119
 120
 121
 122
 123
 124
 125
 126
 127
 128
 129
 130
 131
 132
 133
 134
 135
 136
 137
 138
 139
 140
 141
 142
 143
 144
 145
 146
 147
 148
 149
 150
 151
 152
 153
 154
 155
 156
 157
 158
 159
 160
 161
 162
 163
 164
 165
 166
 167
 168
 169
 170
 171
 172
 173
 174
 175
 176
 177
 178
 179
 180
 181
 182
 183
 184
 185
 186
 187
 188
 189
 190
 191
 192
 193
 194
 195
 196
 197
 198
 199
 200
 201
 202
 203
 204
 205
 206
 207
 208
 209
 210
 211
 212
 213
 214
 215
 216
 217
 218
 219
 220
 221
 222
 223
 224
 225
 226
 227
 228
 229
 230
 231
 232
 233
 234
 235
 236
 237
 238
 239
 240
 241
 242
 243
 244
 245
 246
 247
 248
 249
 250
 251
 252
 253
 254
 255
 256
 257
 258
 259
 260
 261
 262
 263
 264
 265
 266
 267
 268
 269
 270
 271
 272
 273
 274
 275
 276
 277
 278
 279
 280
 281
 282
 283
 284
 285
 286
 287
 288
 289
 290
 291
 292
 293
 294
 295
 296
 297
 298
 299
 300
 301
 302
 303
 304
 305
 306
 307
 308
 309
 310
 311
 312
 313
 314
 315
 316
 317
 318
 319
 320
 321
 322
 323
 324
 325
 326
 327
 328
 329
 330
 331
 332
 333
 334
 335
 336
 337
 338
 339
 340
 341
 342
 343
 344
 345
 346
 347
 348
 349
 350
 351
 352
 353
 354
 355
 356
 357
 358
 359
 360
 361
 362
 363
 364
 365
 366
 367
 368
 369
 370
 371
 372
 373
 374
 375
 376
 377
 378
 379
 380
 381
 382
 383
 384
 385
 386
 387
 388
 389
 390
 391
 392
 393
 394
 395
 396
 397
 398
 399
 400
 401
 402
 403
 404
 405
 406
 407
 408
 409
 410
 411
 412
 413
 414
 415
 416
 417
 418
 419
 420
 421
 422
 423
 424
 425
 426
 427
 428
 429
 430
 431
 432
 433
 434
 435
 436
 437
 438
 439
 440
 441
 442
 443
 444
 445
 446
 447
 448
 449
 450
 451
 452
 453
 454
 455
 456
 457
 458
 459
 460
 461
 462
 463
 464
 465
 466
 467
 468
 469
 470
 471
 472
 473
 474
 475
 476
 477
 478
 479
 480
 481
 482
 483
 484
 485
 486
 487
 488
 489
 490
 491
 492
 493
 494
 495
 496
 497
 498
 499
 500
 501
 502
 503
 504
 505
 506
 507
 508
 509
 510
 511
 512
 513
 514
 515
 516
 517
 518
 519
 520
 521
 522
 523
 524
 525
 526
 527
 528
 529
 530
 531
 532
 533
 534
 535
 536
 537
 538
 539
 540
 541
 542
 543
 544
 545
 546
 547
 548
 549
 550
 551
 552
 553
 554
 555
 556
 557
 558
 559
 560
 561
 562
 563
 564
 565
 566
 567
 568
 569
 570
 571
 572
 573
 574
 575
 576
 577
 578
 579
 580
 581
 582
 583
 584
 585
 586
 587
 588
 589
 590
 591
 592
 593
 594
 595
 596
 597
 598
 599
 600
 601
 602
 603
 604
 605
 606
 607
 608
 609
 610
 611
 612
 613
 614
 615
 616
 617
 618
 619
 620
 621
 622
 623
 624
 625
 626
 627
 628
 629
 630
 631
 632
 633
 634
 635
 636
 637
 638
 639
 640
 641
 642
 643
 644
 645
 646
 647
 648
 649
 650
 651
 652
 653
 654
 655
 656
 657
 658
 659
 660
 661
 662
 663
 664
 665
 666
 667
 668
 669
 670
 671
 672
 673
 674
 675
 676
 677
 678
 679
 680
 681
 682
 683
 684
 685
 686
 687
 688
 689
 690
 691
 692
 693
 694
 695
 696
 697
 698
 699
 700
 701
 702
 703
 704
 705
 706
 707
 708
 709
 710
 711
 712
 713
 714
 715
 716
 717
 718
 719
 720
 721
 722
 723
 724
 725
 726
 727
 728
 729
 730
 731
 732
 733
 734
 735
 736
 737
 738
 739
 740
 741
 742
 743
 744
 745
 746
 747
 748
 749
 750
 751
 752
 753
 754
 755
 756
 757
 758
 759
 7510
 7511
 7512
 7513
 7514
 7515
 7516
 7517
 7518
 7519
 7520
 7521
 7522
 7523
 7524
 7525
 7526
 7527
 7528
 7529
 7530
 7531
 7532
 7533
 7534
 7535
 7536
 7537
 7538
 7539
 7540
 7541
 7542
 7543
 7544
 7545
 7546
 7547
 7548
 7549
 7550
 7551
 7552
 7553
 7554
 7555
 7556
 7557
 7558
 7559
 7560
 7561
 7562
 7563
 7564
 7565
 7566
 7567
 7568
 7569
 7570
 7571
 7572
 7573
 7574
 7575
 7576
 7577
 7578
 7579
 7580
 7581
 7582
 7583
 7584
 7585
 7586
 7587
 7588
 7589
 7590
 7591
 7592
 7593
 7594
 7595
 7596
 7597
 7598
 7599
 75100
 75101
 75102
 75103
 75104
 75105
 75106
 75107
 75108
 75109
 75110
 75111
 75112
 75113
 75114
 75115
 75116
 75117
 75118
 75119
 75120
 75121
 75122
 75123
 75124
 75125
 75126
 75127
 75128
 75129
 75130
 75131
 75132
 75133
 75134
 75135
 75136
 75137
 75138
 75139
 75140
 75141
 75142
 75143
 75144
 75145
 75146
 75147
 75148
 75149
 75150
 75151
 75152
 75153
 75154
 75155
 75156
 75157
 75158
 75159
 75160
 75161
 75162
 75163
 75164
 75165
 75166
 75167
 75168
 75169
 75170
 75171
 75172
 75173
 75174
 75175
 75176
 75177
 75178
 75179
 75180
 75181
 75182
 75183
 75184
 75185
 75186
 75187
 75188
 75189
 75190
 75191
 75192
 75193
 75194
 75195
 75196
 75197
 75198
 75199
 75200
 75201
 75202
 75203
 75204
 75205
 75206
 75207
 75208
 75209
 75210
 75211
 75212
 75213
 75214
 75215
 75216
 75217
 75218
 75219
 75220
 75221
 75222
 75223
 75224
 75225
 75226
 75227
 75228
 75229
 75230
 75231
 75232
 75233
 75234
 75235
 75236
 75237
 75238
 75239
 75240
 75241
 75242
 75243
 75244
 75245
 75246
 75247
 75248
 75249
 75250
 75251
 75252
 75253
 75254
 75255
 75256
 75257
 75258
 75259
 75260
 75261
 75262
 75263
 75264
 75265
 75266
 75267
 75268
 75269
 75270
 75271
 75272
 75273
 75274
 75275
 75276
 75277
 75278
 75279
 75280
 75281
 75282
 75283
 75284
 75285
 75286
 75287
 75288
 75289
 75290
 75291
 75292
 75293
 75294
 75295
 75296
 75297
 75298
 75299
 75300
 75301
 75302
 75303
 75304
 75305
 75306
 75307
 75308
 75309
 75310
 75311
 75312
 75313
 75314
 75315
 75316
 75317
 75318
 75319
 75320
 75321
 75322
 75323
 75324
 75325
 75326
 75327
 75328
 75329
 75330
 75331
 75332
 75333
 75334
 75335
 75336
 75337
 75338
 75339
 75340
 75341
 75342
 75343
 75344
 75345
 75346
 75347
 75348
 75349
 75350
 75351
 75352
 75353
 75354
 75355
 75356
 75357
 75358
 75359
 75360
 75361
 75362
 75363
 75364
 75365
 75366
 75367
 75368
 75369
 75370
 75371
 75372
 75373
 75374
 75375
 75376
 75377
 75378
 75379
 75380
 75381
 75382
 75383
 75384
 75385
 75386
 75387
 75388
 75389
 75390
 75391
 75392
 75393
 75394
 75395
 75396
 75397
 75398
 75399
 75400
 75401
 75402
 75403
 75404
 75405
 75406
 75407
 75408
 75409
 75410
 75411
 75412
 75413
 75414
 75415
 75416
 75417
 75418
 75419
 75420
 75421
 75422
 75423
 75424
 75425
 75426
 75427
 75428
 75429
 75430
 75431
 75432
 75433
 75434
 75435
 75436
 75437
 75438
 75439
 75440
 75441
 75442
 75443
 75444
 75445
 75446
 75447
 75448
 75449
 75450
 75451
 75452
 75453
 75454
 75455
 75456
 75457
 75458
 75459
 75460
 75461
 75462
 75463
 75464
 75465
 75466
 75467
 75468
 75469
 75470
 75471
 75472
 75473
 75474
 75475
 75476
 75477
 75478
 75479
 75480
 75481
 75482
 75483
 75484
 75485
 75486
 75487
 75488
 75489
 75490
 75491
 75492
 75493
 75494
 75495
 75496
 75497
 75498
 75499
 75500
 75501
 75502
 75503
 75504
 75505
 75506
 75507
 75508
 75509
 75510
 75511
 75512
 75513
 75514
 75515
 75516
 75517
 75518
 75519
 75520
 75521
 75522
 75523
 75524
 75525
 75526
 75527
 75528
 75529
 75530
 75531
 75532
 75533
 75534
 75535
 75536
 75537
 75538
 75539
 75540
 75541
 75542
 75543
 75544
 75545
 75546
 75547
 75548
 75549
 75550
 75551
 75552
 75553
 75554
 75555
 75556
 75557
 75558
 75559
 75560
 75561
 75562
 75563
 75564
 75565
 75566
 75567
 75568
 75569
 75570
 75571
 75572
 75573
 755

103
 104
 105
 106
 107
 108
 109
 110
 111
 112
 113
 114

Date	Monday / Tuesday / Wednesday / Thursday / Friday / Saturday/ Sunday		
Time	Food & Beverage	Quantity	Note
Breakfast (: am)			
Morning Tea (: am)			
Lunch (: pm)			
Afternoon Tea (: pm)			
Dinner (: pm)			
Supper (: pm)			
Date	Monday / Tuesday / Wednesday / Thursday / Friday / Saturday/ Sunday		
Time	Food & Beverage	Quantity	Note
Breakfast (: am)			
Morning Tea (: am)			
Lunch (: pm)			
Afternoon Tea (: pm)			
Dinner (: pm)			
Supper (: pm)			

115

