The FreeStyle Libre Pro CGM system consists of a disposable sensor, an applicator, and a reader; that is used to start the sensor on the participant and gather the glucose data at the end of the CGMS period. The Sensor can be worn for up to 14 days, on the back of their upper arm (Figure 7). Once applied, a sensor will measure and store glucose readings every 15 minutes. The 24-hour CGMS does not require any participant action as calibration for the sensor is not needed. Readings from the 24-hour CGMS will not be made available to participants in real time, hence, it will prevent the bias that may arise from unmasked real-time glucose readings. The data from all the 24-hour CGMS (Freestyle Libre Pro, Abbott, Germany) sensors is easily accessible through the FreeStyle Libre Pro Software or The LibreView Cloud. In the present study, the 24-hour CGMS reading will be taken 14-day prior to second visit/second-round OGTT reading. All the data from 24-hour CGMS will be analyzed to

investigate to obtain the optimal-meal-timing. The 24-hour CGMS data will be match with 3-day food diary too.

Exposure measures Meal-timing and chrononutrition

At the baseline visit, the researcher will guide the participants to fill out the 3-day food diary covering two weekdays and one weekend day (consecutive Sunday-Tuesday or Thursday-Saturday). Three-day food diary will be taken twice in the entire study. At the baseline visit, 3-day food diary will be interviewed by researcher to the participants. This food diary data will be served as baseline meal-timing data. Subsequently, participant will be given another 3-days daily dietary at second visit, 14-day prior to third visit. Participants are required to record the time, type, description and number of foods and beverages consumed throughout the day. Brand information, ingredients and cooking method will be recorded where applicable, particularly for home-cooked food. Pictures of household measuring utensils and various food portion sizes are printed in the food diary to assist participants in quantifying their food intake. For 14 day return the CGMS, researcher will be interviewed participants on the completeness of 3 days daily dietary intake.

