pattern from the validated questionnaires PSIQ and light exposure from the validated questionnaire HLEQ.

Statistical Analysis

All data will be performed statistical analysis using the SPSS software version 20 (SPSS Inc., Chicago, IL, USA). The socio-demographic will be presented as mean, standard deviations, median, interquartile range, frequency, and percentage. Data cleaning will be performed to exclude the outlier data before the normality is checked using Kolmogorov-Smirnov Test. The investigator considered $p < 0.05$ to be statistically significant. Chronotype, sleep quality, and light exposure will be analyzed as categorical variables whereas dietary intake, chrononutrition, anthropometry, glycemic measure, and physical activity will be analyzed as continuous variables.

The investigator will perform a multivariable generalized linear model to examine the association between night meal pattern (last night mealtime either dinner or supper with calories intake, frequency of night snacking, and the total number of the night snacking) and glycemic outcome (HbA1c, FPG, 2hPPG, CGM profile) by adjusting for the potential covariates. Specifically, nighttime will be characterized by the time range from 1900 and 0659 hours based on Malaysia solar time. The investigator will explore the late-night meal timing in 2000, 2100, and 2200 to examine its association with glycemic outcomes. The potential confounders include sociodemographic characteristics, physical activity, sleep pattern, sedentary behavior, diet quality, and light exposure will be controlled. ANCOVA test will be performed to understand the association between chrononutrition (breakfast skipping, meal frequency, eating window, sleep timing, chronotype, and fasting pattern) with glycemic variables, controlling for potential covariates (sociodemographic characteristics, light exposure, diet quality, physical activity and sleep pattern).

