APPENDIX I**Chrononutrition Profile Questionnaire**

364

365

366

367

Project Name:

Meal Timing and Glucose Tolerance

Date of interview:

		/				/				
d	d		m	m	m		y	y	y	y

368

369

370

Chrononutrition Profile – Questionnaire (CP-Q)

371

372 Directions: The following questions are designed to assess the general timing of your eating.
 373 Please choose the one response that best fits your typical behavior and preferences.
 374 The term “eating event” refers to any time you eat something that contains calories. For
 375 example, this could be a meal, a snack, or a drink.

376

If you were entirely free to plan your day,

377

378 A1. What time would you prefer to wake up?

379 Please indicate A.M. or P.M. as part of your response.

380 _____ A.M./P.M.

381

382 A2. How soon after waking up would you prefer to have your first eating event of the day?

383 _____ hours _____ minutes

384

385 A3. How soon before bed would you prefer to stop eating?

386 _____ hours _____ minutes

387

388 A4. What time would you prefer to fall asleep? Please indicate A.M. or P.M. as part of your
 389 response. _____ A.M./P.M.

390

391 B1. On average, in a typical week (a 7-day period), B1. How often do you eat breakfast?

392 _____ 0 days _____ 1 day _____ 2 days _____ 3 days _____ 4 days _____ 5 days
 393 _____ 6 days _____ 7 days

394

395 B2. What is your largest meal of the day?

396 _____ Breakfast _____ Lunch _____ Dinner/Supper

397 _____ Other meal (Please describe: _____)

398

399 B3. How often do you eat a snack after your last meal of the day?

400 _____ 0 days _____ 1 day _____ 2 days _____ 3 days _____ 4 days _____ 5 days _____ 6
 401 days _____ 7 days

402

403 B4. How often do you wake up in the night to eat?

404 _____ 0 days _____ 1 day _____ 2 days _____ 3 days _____ 4 days _____ 5 days _____ 6
 405 days _____ 7 day

406

On average, on a typical workday or school day,

407

408 C1. What time do you wake up?

409 Please indicate A.M./P.M. as part of your response.

410

411 _____ A.M./P.M.

412

415
416 C2. What time is your first eating event of the day?
417 Please indicate A.M./P.M. as part of your response.
418 _____ A.M./P.M.
419
420 C3. What time do you eat lunch?
421 Please indicate A.M./P.M. as part of your response.

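### The three-day diary has no timed field for an eating occasion beyond six named meals, although the plan asks for every intake to be timed and analyses energy by clock hour

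*Combined protocol and SAP*

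**What the plan says.** **The form (Appendix E).** All three diary days carry the same six rows: breakfast, morning tea, lunch, afternoon tea, dinner and supper. The time blank sits inside the meal label, as in "Morning Tea (: am" and "Afternoon Tea (: pm". The other columns, headed "Food & Beverage", quantity and note, carry no time. No open or untitled timed row is printed.

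**The instructions.** Guideline 3 on the form reads: "please indicate the time, type and quantity/ size of all food and beverages taken immediately after meal time". The Methodology section on meal timing and chrononutrition likewise asks for the time of foods and drinks over the whole day.

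**The planned uses.** The Methodology takes the second diary day and tabulates energy and macronutrients in five periods and by clock hour. It also says: "The 24-hour CGMS data will be match with 3-day food diary too". The sensor stores a reading every 15 minutes. Under Statistical Analysis, the ANCOVA exposures include "breakfast skipping, meal frequency, eating window". No definition, source instrument or minimum interval is given for meal frequency.

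**Nearby wording in other instruments.** In the Chrononutrition Profile Questionnaire (Appendix I), an eating event "refers to any time you eat something that contains calories". In Appendix B, item 2.8, on snacks after 7 pm: "Snacking frequency is defined with a time interval between episodes of at least 15 min".

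**The concern.** Meal timing is the exposure of this study, and the diary is the only instrument that records foods, amounts and clock times together. Two snacks between lunch and dinner, or several sweetened drinks in a morning, have one time blank between them.

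Two analyses could be affected. First, energy from merged occasions is placed at one clock time, so it can fall in the wrong hour or period and be set against the wrong stretch of the sensor trace. Second, if meal frequency is counted as filled rows, frequent eaters are drawn towards everyone else, which weakens any association with the glycemic outcomes.

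**Working it through.** **1. Form against use.** Six time blanks a day over three days gives 6 × 3 = 18 per diary. Only the second day is analysed, so at most 6 printed times per participant per diary feed the hourly tabulation. The instruction sets no such limit. The supper blank is pre-marked pm, yet the first of the five periods runs from 00:00 to 04:49, so intake after midnight has no clean entry either.

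**2. Is the diary the source of meal frequency?** The plan does not say. The alternatives are weak. Appendix I asks for days per week with breakfast, with a snack after the last meal and with waking to eat, plus first, lunch and last eating times; it yields no daily count. Appendix B item 2.8 covers only snacks after 7 pm. The light questionnaire (Appendix G) has meal hours circled on an hourly grid, without food or energy. The diary is the likely source of meal frequency (an inference) and the stated source of timed energy.

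**3. How large could the compression be?** The plan has no figure to reproduce, and the documents give no eating rates, so every rate below is an assumption.

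*(a) Limit on the daily total.* Let the true daily count be K ~ Poisson(m) and the recorded count be C = min(K, 6). The share of days affected is P(K > 6), and the correlation is Cov(K, C) / √(m · Var C).

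| Mean m | Days above 6 | Mean of C | Correlation of C with K |
|---|---|---|---|
| 3 | 3% | 2.95 | 0.99 |
| 4 | 11% | 3.80 | 0.95 |
| 5 | 24% | 4.51 | 0.90 |
| 6 | 39% | 5.04 | 0.83 |
| 7 | 55% | 5.41 | 0.74 |

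*(b) Limit of one time per slot.* Part (a) is lenient, because two afternoon snacks can collapse on a day with only five occasions. Assume one row for each of three between-meal gaps, with Poisson mean λ per gap. A gap merges nothing with probability e^(−λ)(1 + λ), so the share of days with at least one merger is 1 − [e^(−λ)(1 + λ)]³:

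- λ = 0.3: 1 − 0.963³ = 11%
- λ = 0.6: 1 − 0.878³ = 32%
- λ = 1.0: 1 − 0.736³ = 60%

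Letting people differ (a gamma multiplier of shape 2 shared across gaps, with main meals eaten on 80%, 95% and 95% of days), simulation gives 12%, 31% and 50% of days. The recorded count then correlates 0.93, 0.85 and 0.78 with the true count.

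Both models run from minor to material, and nothing in the documents selects a row.

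**The case against.** The strongest reply is that the printed rows do not fix what is recorded. The instructions ask for all times, and the food and note cells leave room to write them. The baseline diary is gone through by interview, completeness is checked by interview when the sensor is returned, and phone follow-up is planned. This stands, so the documents do not establish that extra occasions are lost. But nothing tells participants to write extra times in those cells, no coding rule would extract them, and the return interview is described as a check of completeness, not of timing.

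A reader might infer that meal frequency is capped at six. The documents do not support that. They name no source or counting rule, so the limit belongs to the printed rows and reaches the variable only if filled rows are counted.

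A reader might also infer that the diary breaches the plan's own definition of an eating occasion. There is none for the diary or the analysis. The calorie-based eating event and the 15-minute interval belong to two other instruments.

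Nor does the point extend to every listed exposure. Eating window can be taken from the first and last eating times in Appendix I (C2, C4, D2, D4), and merging snacks between meals does not move the first or last time. Night snacking has its own items in Appendix B (2.8) and Appendix I (B3, B4).

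**Conclusion.** The point holds in limited form. The diary has no timed field for a further eating occasion. That conflicts with the instruction to time all intake and with the hourly, five-period and sensor-matched uses of the diary. Occasions within a slot are merged unless the participant or interviewer adds a time. The main exposure is to timed daytime energy and, if counted from filled rows, to meal frequency.

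The size is not determined by the documents. Under the assumed rates in (a), the correlation of recorded with true frequency runs from 0.99 to 0.74. Converting this into lost power would be tempting but is unsupported: it needs eating rates that the plan does not give, and the plan's effect size of 0.13 was adopted from a late-night-dinner cohort, not for meal frequency.

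The reading assumes that no unlabelled blank row follows supper on the printed page. All three days show the same six rows, so a lost row is unlikely, but the page should be checked.

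**What to change.** - **Form.** Keep the six named meals as prompts. Add several untitled rows per day, each with a 24-hour time field, and instruct one row per eating or drinking occasion that contains calories.
- **Analysis plan.** State that meal frequency and timed energy are derived from these rows, with a stated minimum interval between occasions; the 15 minutes in Appendix B item 2.8 is one candidate.
- **Interviews.** Use the diary interviews already planned to ask for missed occasions and their times.
- **Diaries already on the six-row form.** The document is dated 6 May 2024, and its milestones complete the third visit by 31/03/2024, so reprinting may come too late for this cohort. In that case, code any extra times written in the other cells, fix the counting rule before analysis, and report the form's limit.

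The cost is a reprinted page and slightly more coding per diary day. For collected diaries it is coding and a sentence in the report.
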